7.4 Outcome variables

7.4.1 Primary outcome variables

- Changes in CEC density.
- IOP.

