7.4.2 Secondary outcome variables

- Incidence of adverse events.
- Changes in corneal thickness.
- Cellularity in AC.
- Flare in AC.
- Best corrected visual acuity

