7.4.4.1 Corneal endothelial cell density

Specular microscopy allows a clear view of live endothelial cells without altering their function or morphology. In turn, a surface area count can be performed to determine if there is an alteration in the shape or size of the endothelial cells, parameters that must be taken into account to determine the functional capacity of the corneal endothelium. CEC density decreases over time, due to diseases and intraocular surgical procedures. Analysis of CEC density will be performed using a specular microscope

(the make and model of the equipment must be specified). The density in cells/mm² will be recorded in the eCRF. The area and strategy used in the scrutiny visit must be the same as the final visit.

Management as AE: This value, by itself, will not be considered an AE regardless of the changes; the AE will correspond in each case to a clinical corneal decompensation when so judged by the PI.

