7.4.4.2 Intraocular pressure

Tonometry is the objective measure of IOP, based primarily on the force required to flatten the cornea, or the degree of corneal depression produced by a fixed force. Goldman tonometry is based on the Imbert-Fick principle. [34]

Tonometry will be performed after instillation of topical anesthetic with fluorescein and the use of a cobalt blue filter (after assessing surface staining). Two readings will be taken, and the average will be recorded in the clinical record. The average will be recorded in the eCRF.

Management as AE: IOP peaks ≥ 30 mmHg should be reported as AE.

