7.4.4.3 Adverse events

As described in section 8.2, an adverse event is defined as Any adverse medical occurrence in a subject to whom an investigational product is administered, regardless of causal attribution.

The management of adverse events will be carried out in accordance with the provisions of Section 8. Evaluation and management of adverse events and incidents.

Any adverse events that study subjects experience will be reported by the PI in the corresponding section of the eCRF and also in the clinical record.

For an adequate assessment of adverse events, in addition to the targeted questioning, a Comprehensive Ophthalmologic Evaluation must be performed at each visit. This evaluation consists of: ophthalmologic examination of the eyelids and adnexa; anterior and posterior segments, which are performed during a routine ophthalmologic examination, procedures not specifically included in the study variables. The posterior pole evaluation may be performed with direct or indirect ophthalmoscopy, with or without pharmacological mydriasis, at the discretion of the PI. The fundus will be assessed for abnormalities that could alter the study results. IOP will be measured during this evaluation, using the PI's chosen instrument, and should be measured after the stain evaluation. The results of the evaluation will be recorded in the clinical record. Only those findings that the Principal Investigator considers to be adverse events will be reported in the eCRF.

Adverse events (including incidents, adverse events) that may occur with the use of PRO-149 or Healon® EndoCoat medical devices are: ocular inflammation (iritis, hypopyon, endophthalmitis), increased intraocular pressure, corneal edema, secondary glaucoma, corneal decompensation, cystoid macular edema, blurred vision, burning, ocular pain, ocular irritation, breakage of intraocular lens haptics, foreign body on ocular surface.

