8.3 Use of adverse events as a study safety variable

Measuring the safety of PRO-149 use is paramount to the study, therefore, it is considered important to report any undesirable manifestation or illness that occurs during the course of the study, regardless of whether the manifestation is considered related to the investigational treatment or not. [40]

Reporting all adverse events occurring during the investigation will allow us to subsequently determine their causality to the investigational treatment (medical devices) and determine whether they are incidents or adverse events; or determine their causality to concomitant medical treatment or other procedures. [36, 37, 38, 39, 40, 41]

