10.1.2 Data interpretation

The results of continuous quantitative variables will be presented in measures of central tendency: mean, standard deviation and ranges.

KS and SW tests will be performed, as applicable, to determine whether the distribution presents normality in the results obtained in each study group. [44]

If normality of the data is observed ($p > 0.05$; for KS and SW), the statistical analysis of the continuous quantitative variables to find significant differences (p) will be as follows:

- Intra-group analysis: will be determined using the Student's t-test for repeated measures.
- Between-group analysis: differences between groups will be analyzed using Student's t-test for independent groups.

For $p < 0.05$ in KS and SW, the statistical analysis of continuous quantitative variables to find significant differences (p) will be as follows:

- Intra-group analysis: will be determined using the Wilcoxon rank test. [45]
- Between-group analysis: differences between groups will be analyzed using the Mann-Whitney U statistic.

The level of difference to consider significance will be an α of 0.05 or less [46].

The results of the nominal and ordinal qualitative variables will be presented in frequencies, proportions and percentages.

Statistical analysis to identify significant differences in qualitative variables will be performed by creating 2x2 contingency tables and will be carried out as follows:

- Intra-group differences: will be determined by the McNemar test [47], which is applied to 2x2 contingency tables with a dichotomous trait and pairs of matched subjects to determine whether the marginal frequencies of row and column are equal (marginal homogeneity).
- Difference between groups: Differences between groups will be analyzed using Pearson's X^2 test or Fisher's exact test when expected values are less than 5.

The level of difference to consider significance will be an α of 0.05 or less.

For the reporting of adverse events, participants who were randomly assigned to an intervention group after application of the investigational product will be considered.

The final results report will be displayed in tables or graphs, as appropriate.

The investigational product will be considered safe when there are no clinical and statistical differences in all primary outcome variables, with respect to its comparator (Healon EndoCoat®).

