11.3 Early termination of the study

The study may be temporarily suspended or terminated prematurely if there is sufficiently reasonable cause. Written notification documenting the reason for the suspension or early termination must be provided by the party executing the suspension. The PI must promptly inform the study participants, the IC, and the IRB, providing the reasons.

Situations in which suspension or early termination of the study will be considered include, but are not limited to:

1. The presence of serious adverse events in more than 10% of participants in a study group.
2. The regulatory authority (COFEPRIS) considered it due to security alerts.
3. The Sponsor determines this for its convenience or eventualities such as: financial support, manufacturing errors, etc.
4. The determination of unexpected risks to participants that are significant or unacceptable.
5. Obtaining new relevant safety information.
6. Insufficient adherence to protocol requirements.
7. The data obtained are not evaluable or are not sufficiently complete.
8. The determination that the primary objective has been achieved.
9. The determination of futility.

In the event of suspension, the study may be resumed once the situations that led to the suspension have been resolved, provided this justification is sufficient for the sponsor, IC, IEC, and regulatory authorities.

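### The only rule for calling PRO-149 safe rests on CEC change and IOP; adverse events count only where they show up in those two measurements

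*Combined protocol and SAP*

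**What the plan says.** The last sentence of section 10.1.2 reads: "The investigational product will be considered safe when there are no clinical and statistical differences in all primary outcome variables", with Healon EndoCoat as the reference. Section 7.4.1 lists two primary variables: "Changes in CEC density" and IOP. Section 7.4.2 makes "Incidence of adverse events" secondary, together with corneal thickness, anterior chamber cellularity, flare and best corrected visual acuity.

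The primary objective (3.1) is the safety of PRO-149 against the comparator, and H1 (3.5) states equivalence of safety without limiting it to two measurements. Section 8.3, which makes adverse events a safety variable, says: "Measuring the safety of PRO-149 use is paramount to the study". Section 7.4.4.3 lists events that may occur with either device, among them "ocular inflammation (iritis, hypopyon, endophthalmitis), increased intraocular pressure, corneal edema, secondary glaucoma, corneal decompensation".

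Three passages connect adverse events with the primary variables or with the course of the trial:
- Section 7.4.4.2: "IOP peaks ≥ 30 mmHg should be reported as AE".
- Section 7.4.4.1, on CEC density: "This value, by itself, will not be considered an AE regardless of the changes". The adverse event is clinical corneal decompensation as judged by the investigator.
- Section 11.3 gives, among the grounds on which suspension or early termination will be considered: "The presence of serious adverse events in more than 10% of participants in a study group".

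**The concern.** Section 2.3.1 states that there are no clinical trial data on PRO-149, and the trial's headline result will be whether the product may be called safe. The rule that settles this leaves out the events that the protocol itself names as hazards of the device class. A hypopyon or endophthalmitis judged related to the device would be recorded, tabulated and reported, but the sentence in 10.1.2 gives it no part in the verdict. Where the rule errs for this reason, it errs toward declaring safety.

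This is separate from whether the rule is a proper equivalence test. A correct margin test on CEC change and IOP would still leave adverse events out.

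**Working it through.** The plan gives no figure for this rule, so the check is mainly a reading of the text. The arithmetic shows how much the indirect routes can carry.

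**1. What can reach the verdict.**

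| Finding | Where it is handled | Tied to the verdict in 10.1.2? |
|---|---|---|
| CEC change, IOP | 7.4.1, primary | Yes |
| Adverse event incidence | 7.4.2; compared by chi-square or Fisher, or as counts (Table 3) | No |
| Seriousness, causality | 8.4, 8.5.4; recorded and reported | No |
| Cellularity, flare | 7.4.2; grade 3 or more is an adverse event (7.4.4.5) | No |
| IOP of 30 mmHg or more | 7.4.4.2; an adverse event and also a value of a primary variable | Only through the IOP comparison |
| Corneal decompensation | 7.4.4.1; adverse event | Only if it shows in CEC density |
| Serious events above 10% of a group | 11.3 | No; termination is considered |

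**2. When adverse events leave CEC and IOP unaffected.** Suppose there is no true difference in either variable, each is tested once at 0.05, and the tests are independent (an assumption). The chance that neither is significant is 0.95 × 0.95 = 0.9025. This does not depend on the rate of events that leave CEC and IOP unchanged.

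**3. How strongly IOP spikes enter through the IOP comparison.** Section 10.2.1 gives 18 eyes per arm. The documents give no postoperative IOP mean or standard deviation, so these are assumed: normal non-spike readings at one visit, k PRO-149 eyes replaced by readings from 30 to 35 or 36 mmHg, and no spikes in the comparator arm.

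| Spikes, PRO-149 vs comparator | Assumed mean, SD (mmHg) | t-test, p at most 0.05 | Mann-Whitney, p at most 0.05 |
|---|---|---|---|
| 1 vs 0 | 15, 3-4 | about 4-5% | about 5% |
| 2 vs 0 | 15, 3-4 | about 9-10% | about 7% |
| 3 vs 0 | 15, 3-4 | about 19-21% | about 9-10% |
| 4 vs 0 | 14-16, 2.5-5 | about 29-51% | about 15-18% |

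**4. Whether a significance test on adverse events would close the gap.** For k of 18 against 0 of 18, the two-sided Fisher p is 2 × C(18,k) / C(36,k):
- k = 3: 2 × 816 / 7,140 = 0.229
- k = 4: 2 × 3,060 / 58,905 = 0.104
- k = 5: 2 × 8,568 / 376,992 = 0.045

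So 5 versus 0 is the first split against zero below 0.05. Section 2.2.2 gives a rate of 10.5% for IOP of 30 mmHg or more with the comparator. Exact Fisher power at 18 per arm is 6.5% for 21% versus 10.5% (a doubling) and 22% for 31.5% versus 10.5% (a tripling). With 0 of 18 events, the one-sided 95% upper bound is 1 − 0.05^(1/18) = 15.3%. Requiring no significant adverse event difference would therefore add little.

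**5. The 11.3 threshold.** 1/18 = 5.6% and 2/18 = 11.1%, so two subjects with serious events in a full arm pass the 10% mark. The text then says that suspension or termination will be considered. It does not say what is concluded if the trial continues to the end.

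**6. The CEC route can also close.** Table 3 has CEC density measured only at the scrutiny and final visits. Section 5.2.1 allows a subject to be eliminated for an adverse event, and 10.1.5 bases the analysis for the study objective on subjects who complete all visits. An eye with a serious event may thus be missing from the CEC comparison. Section 10.1.3 puts all exposed subjects in the safety assessment but attaches no criterion to it.

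**The case against.** The strongest case for the plan has four parts.

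First, adverse events are not wholly outside the rule. An IOP of 30 mmHg or more is a value of a primary variable, and in the comparator study described in 2.2.2 it made up 92% of adverse events. Corneal damage can show in CEC density. This stands, and it rules out the reading that no adverse event can affect the conclusion. The routes are weak, however, and exist only for events that leave a mark on these two measurements.

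Second, 11.3 provides for serious events, significant unexpected risks and new safety information. A reader might infer that the plan is bound to call PRO-149 safe even after several endophthalmitis cases in its arm. The documents do not support that, since such cases could plausibly lead to termination before any verdict. But 11.3 is discretionary and does not alter the rule for a completed trial.

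Third, the rule asks for no clinical as well as no statistical difference, so four eyes against none with a spike could be judged a clinical difference whatever the p-value. That is fair for IOP, although the term is not defined. It does not bring in other events, because the phrase is confined to the primary variables.

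Fourth, the layout is a deliberate choice. Section 3.2 defines the main safety comparisons through CEC and IOP, 3.3 makes adverse events a secondary safety objective, and all events are to be reported. That choice is legitimate for the comparisons. It does not justify a conclusion about the safety of the product as a whole drawn from those two variables alone.

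**Conclusion.** The point holds in a limited form. The plan's only rule for the word safe gives no weight to adverse event incidence, seriousness or causality, or to cellularity or flare, except where an event appears in the IOP or CEC data. It answers a narrower question than 3.1 and 3.5 ask, and it does not fit the importance that 8.3 gives to safety.

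This conclusion rests on the text and needs no assumption. The size of the IOP route does: the 30-50% (t-test) and 15-18% (Mann-Whitney) for 4 versus 0 spikes depend on assumed IOP distributions and on a single visit, whereas IOP is measured at three postoperative visits and the documents do not say which one decides. The Fisher values are exact for 18 per arm; they bear on the choice of remedy and do not measure the defect.

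A reader might also take PRO-149 never to have been used in humans. Section 2.3.1 says only that there are no prior clinical trial data.

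The point should be settled before the analysis, because it concerns the main conclusion and can lead to safety being declared too readily.

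**What to change.** Amend the last sentence of 10.1.2 in one of two ways.

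*Preferred.* Word the conclusion as what was tested, namely the comparison of CEC change and IOP between PRO-149 and Healon EndoCoat, and do not call the product as a whole safe on that basis alone. Adverse events, cellularity and flare are reported beside it.

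*Alternative.* Keep the word safe, but make it depend also on a by-arm review, in all exposed subjects, of serious adverse events, adverse events judged at least possibly related, IOP of 30 mmHg or more, cellularity or flare of grade 3 or more, and corneal decompensation. Report counts with confidence intervals for the difference, and do not judge them by p-value. State beforehand who conducts the review and what would count as a clinically relevant excess.

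In either case, say how the conclusion relates to 8.3 and to the grounds in 11.3.

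The cost is one sentence and a listing of data already collected. A favourable conclusion becomes narrower (preferred) or slightly harder to reach (alternative). The alternative also brings causality judgements made by unblinded investigators into the verdict, which is why the first option is preferable.

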2.2.1 Efficacy of the investigational product

The efficacy of various SH-containing OVDs has been established in several clinical studies. A multicenter, double-blind, randomized clinical study was conducted with the Healon® EndoCoat OVD, which contains the same concentration of SH as PRO-149, in 400 patients undergoing phacoemulsification and IOL implantation.

Two hundred patients were assigned to the Healon® EndoCoat group and 200 to the control group, corresponding to Viscoat®. Efficacy was measured by CEC protection. Healon® EndoCoat demonstrated non-inferiority when compared to Viscoat® in the CEC count from pre-surgery to 3 months post-surgery ($p < 0.0001$, 1-tailed t-test, $\delta = 5\%$). The mean percentage changes observed were -4.7% for Healon® EndoCoat and -7.0% for Viscoat® with a percentage point difference of 2.3 (90% confidence interval: [0.23, 4.33]). [21]

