3.5 Hypothesis

H_1 : PRO-149 viscoelastic solution is equivalent in safety to Healon® EndoCoat for use as an OVD in phacoemulsification surgery and IOL placement in patients with senile cataracts.

H_0 : PRO-149 viscoelastic solution is not equivalent in safety to Healon® EndoCoat for use as an OVD in phacoemulsification surgery and IOL placement in patients with senile cataract.

4. Study design

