10.2.2 Justification of the sample calculation

Although there are no references on sample size calculation for pilot studies, it was considered appropriate to perform the calculation based on the clinical study by Storr-Paulsen et al [48], who compared the influence of three OVDs of 1%, 2% and 3% SH on corneal endothelial cell count during cataract surgery up to three months postoperatively. All three OVDs showed a decrease in postoperative cell count, for SH-1% it was 18.46%, for SH-2% it was 18.03% and for SH-3% it was 6.97%. [48]

The percentage decrease in dispersive OVD at 3% SH was considered. The sample size was calculated using the equation for an equivalence ratio [49], which is useful when we want to test whether a ratio p , is different from a standard reference value, p_0 . In this case, we want to test that PRO-149 is equivalent to its comparator (Healon® EndoCoat). Here the test falls on PRO-149; that is, equivalence is represented by the alternative hypothesis (H_1), rather than the null hypothesis (H_0).

Working hypothesis for calculating the sample size:

$$H_0: |P - P_0| \geq \delta$$
$$H_1: |P - P_0| < \delta$$

Considering an $\alpha = 0.05$ corresponding to the type I error (95% confidence level), a power (β) = 0.20 corresponding to the type II error (80% power) and a test margin (δ) of 5%. The calculation to estimate the sample size was performed using an online tool (*Sample size calculators*, <http://powerandsamplesize.com>), following the following equations:

$$n = p(1-p) \left(\frac{Z_{1-\alpha} + Z_{1-\beta/2}}{|p - p_0| - \delta} \right)^2$$

$$1 - \beta = 2[\Phi(z - z_{1-\alpha}) + \Phi(-z - z_{1-\alpha})] - 1, z = \frac{|p - p_0| - \delta}{\sqrt{\frac{p(1-p)}{n}}}$$

Where:

n: sample size,

p₀: comparison value,

Φ: function of the standard normal distribution

Φ⁻¹: normal standard quantile function

α: Type I error

β: Type II error (1-β is the power)

δ: test margin.

According to the previous calculation, the result was 14 cases (eyes) per arm; this calculation was increased by 20% to account for potential losses. The total sample size required is 18 cases (eyes) per treatment arm, a total of 36 cases. This calculation is consistent with the sample size used in similar clinical studies where OVDs were employed. [50, 51, 52]

11. Ethical considerations

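### The rule for calling PRO-149 safe has no direction, so a clear endothelial advantage over EndoCoat would count against it

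*Combined protocol and SAP*

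**What the plan says.** The objective in 3.1 is to evaluate the safety of PRO-149 against Healon EndoCoat. The primary outcomes in 7.4.1 are "Changes in CEC density" and IOP.

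The decision statements are these:

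- **Section 3.5, repeated in 1.1.** The alternative hypothesis is "PRO-149 viscoelastic solution is equivalent in safety to Healon® EndoCoat for use as an OVD"; the null is "PRO-149 viscoelastic solution is not equivalent in safety to Healon® EndoCoat for use as an OVD".
- **Section 10.2.2.** The sizing section says "we want to test that PRO-149 is equivalent to its comparator" and writes the null as |P − P0| ≥ δ, with δ = 5%.
- **Section 10.1.2, success rule.** "The investigational product will be considered safe when there are no clinical and statistical differences in all primary outcome variables", with respect to the comparator.
- **Section 10.1.2, test.** For normally distributed data, "differences between groups will be analyzed using Student's t-test for independent groups"; otherwise Mann-Whitney U. "The level of difference to consider significance will be an α of 0.05 or less".

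None of these gives a direction. The term clinical difference is not defined, sidedness is not stated, and no margin is given for IOP.

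The background does use direction. Section 2.2.1 reports that "Healon® EndoCoat demonstrated non-inferiority when compared to Viscoat® in the CEC count from pre-surgery to 3 months post-surgery", on a one-tailed test with a 5% margin. Section 2.2.2 reports that IOP peaks of 30 mmHg or more were not more frequent than with the control device.

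**The concern.** The safety question for CEC runs one way: does PRO-149 cost the patient more endothelial cells than EndoCoat? A rule that requires no difference treats fewer lost cells exactly like more lost cells. Followed to the letter, it withholds the safe conclusion when the new device protects the cornea better, and the chance of that rises with the size of the benefit and with the precision of the data. The hypothesis in 10.2.2 has the same property: a benefit of δ or more sits inside the null. Replacing the difference test with a formal two-sided equivalence test would therefore leave the direction problem in place.

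This rule produces the trial's headline conclusion. If the plan stays silent and a favourable difference appears, the sponsor must either report a failure that makes no sense or reinterpret the rule after seeing the data.

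**Working it through.** **The plan's own figure.** Section 10.2.2 states 14 eyes per arm before losses. Its formula with p = p0 = 0.0697, δ = 0.05, z(0.95) = 1.645 and z(0.90) = 1.282 gives 0.0697 × 0.9303 × (2.926/0.05)² ≈ 222. The 14 is not reproduced at a 5% margin. That is a separate matter; I take the planned 18 per arm as given (14/0.8 = 17.5, rounded up).

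**Inputs**

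- n = 18 per arm (10.2.1); α = 0.05 (10.1.2), taken as two-sided because the tests are described as looking for differences.
- Comparator mean loss: 4.7% for EndoCoat (2.2.1), or 6.97% for the 3% sodium hyaluronate device used for sizing (10.2.2).
- SD of percentage CEC change: not stated. From the 90% CI [0.23, 4.33] with 200 per arm in 2.2.1, SE = (4.33 − 0.23)/(2 × 1.645) = 1.246 and SD = 1.246/√(2/200) = 12.46. This is an assumption: that study ran to 3 months, whereas this trial measures CEC at day 29 ± 2. SD 8 is shown as a smaller alternative.

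**Smallest significant advantage.** With 34 degrees of freedom the critical t is 2.032.

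- SD 12.46: SE = 12.46 × √(2/18) = 4.153; an observed advantage must exceed 2.032 × 4.153 = 8.4 points.
- SD 8: SE = 2.667; it must exceed 5.4 points.

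**Probability that PRO-149 is significantly better on CEC** (upper tail of the non-central t with non-centrality d/SE):

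| True advantage d | SD 12.46 | SD 8 |
|---|---|---|
| 0 | 2.5% | 2.5% |
| 4.7 points (no loss against 4.7%) | 19% | 40% |
| 5 points | 21% | 45% |
| 6.97 points (no loss against 6.97%) | 37% | 72% |

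The rows at 4.7 and 6.97 are ceilings: PRO-149 cannot beat the comparator by more than the comparator's own mean loss unless mean density rises after surgery, and 7.4.4.1 says density falls with intraocular procedures.

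**How the rule's wording affects these figures.** If failure needs both a statistical and a clinical difference, they are upper bounds on failure by this route. If either alone is enough, they are lower bounds. Neither reading supplies a direction.

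**What formal non-inferiority would do.** With a one-sided 5% test and the 5-point margin at SD 12.46 and 18 per arm, a truly equal product passes about 32% of the time. For 80% power, n = 2 × [12.46 × (1.645 + 0.842)/5]² ≈ 77 per arm.

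**The case against.** The strongest reply is that equivalence to a marketed reference is a deliberate choice. Section 2.6 argues that apparently identical devices may behave differently, and this is a pilot. Both devices are 3% sodium hyaluronate from bacterial fermentation (2.2), so a large advantage is unlikely. The error is also conservative: it withholds a favourable label and endangers no participant. All of that stands, and it limits the severity. It does not supply a reason why fewer lost endothelial cells should count against safety.

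Four stronger readings are tempting, and the documents do not support them.

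- **That failure through benefit is likely.** The gap between 1% and 3% sodium hyaluronate in 10.2.2 (18.46 − 6.97 = 11.49 points) might suggest advantages of 10 points or more. That scale comes from a device losing 18.46%, not from this comparator. At SD 12.46, a product truly 5 points better still avoids a significant CEC difference about 78% of the time.
- **That a one-sided test at the same n lifts power from 80% to 90%.** This presumes that the plan's formula delivers 80% at the planned n. It needs 222. At n = 18, z = 0.05/√(0.0697 × 0.9303/18) = 0.83, and one-sided power is Φ(0.83 − 1.645), about 21%.
- **That lower IOP is equally plainly a benefit.** Table 3 gives a normal range of 10 to 21 mmHg, so low values are also abnormal. A two-sided reading is defensible for IOP if the plan states it. The 0.13 margin in 2.2.2 concerns the proportion with peaks, not mean IOP.
- **That non-inferiority is only a change of words.** The 32% pass rate for an equal product shows otherwise.

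By the same symmetry, a product truly 5 points worse also shows no significant difference about 78% of the time. That is graver, but it is a different defect, non-significance read as equivalence, and should not raise the rating here.

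**Conclusion.** The decision rule is wrong as written for CEC. It and the hypotheses behind it have no direction, and nothing in the document rescues a favourable difference, so a product significantly and clinically better on CEC could not be called safe. The contradiction with the objective rests on the text alone. Its size rests on assumptions: a borrowed 3-month SD, normal data, a two-sided test and 18 evaluable eyes per arm. Under them the chance of tripping the rule through benefit is small for near-equal products and has a ceiling of about 19% to 37% at SD 12.5, or 40% to 72% at SD 8. For IOP the defect is only that the harmful direction or directions are not stated. Severity is minor to moderate.

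**What to change.** In 1.1, 3.5, 10.1.2 and 10.2.2:

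1. State that harm on CEC means greater loss with PRO-149 than with EndoCoat, and that a favourable CEC difference does not count against safety.
2. State which direction or directions of IOP difference count as harm. If both do, say so and give the reason.
3. Report the between-group difference with its confidence interval for each primary outcome.

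This is a text amendment with almost no cost if made before data are seen. The trial gives up only the claim that PRO-149 is no better than EndoCoat on CEC, which a safety objective does not need.

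Moving to formal one-sided non-inferiority with the 5-point margin is a larger step. The sponsor would have to disclose that at SD 12.5 and 18 per arm a truly equal product passes only about 32% of the time (about 77 per arm for 80% power), and would have to set and justify an IOP margin.
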